5.2.1.3 Guidance for Diagnosis and Management of Hepatic Events of Clinical Interest

In addition to overdose, hepatic ECIs will include any of the following events. All of these events will require holding study treatment, notification of the Sponsor within 24 hours, and a hepatologist consultation (if necessary). All cases of retreatment and permanent discontinuation must be reported to the Sponsor and recorded in the database. Refer to Section 7.2.3.2 for reporting guidelines and the definition of hepatic ECIs.

a. ALT:

- i. Among subjects with baseline ALT $<2\times$ ULN: ALT $\ge 5\times$ ULN
- ii. Among subjects with baseline ALT $\ge 2 \times ULN$: ALT $> 3 \times$ the baseline level
- iii. ALT >500 U/L regardless of baseline level

Protocol/Amendment No.: 394-06

b. AST:

- i. Among subjects with baseline AST $\leq 2 \times ULN$: AST $\geq 5 \times ULN$
- ii. Among subjects with baseline AST ≥2×ULN: AST >3× the baseline level
- iii. AST >500 U/L regardless of baseline level
- c. Total Bilirubin:
 - i. Among subjects with baseline levels <1.5 mg/dL: a value of >2.0 mg/dL
 - ii. Among subjects with baseline levels that are ≥ 1.5 mg/dL: a value $\ge 2 \times$ the baseline level
 - iii. Total bilirubin >3.0 mg/dL regardless of baseline level
- d. Regardless of laboratory values, hepatic decompensation diagnosed clinically, including:
 - i. New onset clinically detectable ascites
 - ii. Gastrointestinal bleeding suggestive of portal hypertension (e.g., esophageal or gastric varices)
 - iii. Encephalopathy

Immediate assessment

All subjects

- All subjects should be evaluated according to directions below within 72 hours of alert for non-overdose hepatic ECI
- Procedures:
 - Obtain a consultation with a hepatologist (if necessary)
 - Obtain a work-up for hepatitis if there is no underlying hepatitis, including hepatitis A, B,C, D, E, Epstein-Barr virus, and cytomegalovirus
 - Assess for ingestion of drugs/supplements with hepatotoxic potential
 - Assess for alcohol ingestion
 - Assess for potential bacterial infection, biliary obstruction, or occult gastrointestinal bleeding

Product: MK-3475 44

Protocol/Amendment No.: 394-06

• Repeat ALT, AST, T-bil, D-bil, ALP, γ-glutamyl transpeptidase, INR, and complete blood count (CBC) with differential

- o Other laboratories or imaging studies as clinically indicated
- Consider liver biopsy if indicated by hepatologist

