Hepatitis C-Infected Subjects (including subjects who previously achieved sustained virologic response for 12 weeks [SVR 12] or sustained virologic response for 24 weeks [SVR24]

• In addition to the above, measure HCV RNA viral load

Hepatitis B-infected Subjects

- In addition to the above, measure HBV DNA, HBsAg, HBeAg, anti-HBc, anti-HBe antibody, and anti-HBs antibody
- Subjects should be questioned about compliance with the use of anti-viral agents.

Permanent Discontinuation Criteria for Subjects with Non-overdose Hepatic ECI

Therapy should also be permanently discontinued for:

- ALT $>20 \times ULN$
- Child-Pugh (CP) score of ≥9 points
- Gastrointestinal bleeding suggestive of portal hypertension (e.g., esophageal or gastric varices)
- New onset clinically detectable ascites
- Hepatic encephalopathy or
- Recurrence of a severe or life-threatening event, or of any of the laboratory abnormalities listed above, that are presumed to be immune-related.

Protocol/Amendment No.: 394-06

Diagnosis and Management of Non-Overdose Hepatic ECIs

HCC subjects are at risk for a range of complications that can cause hepatic laboratory abnormalities with or without clinical decompensation. Those with a history of chronic HCV or HBV infection also have the potential to experience virologic flares. Immune-related hepatitis has been observed in $\sim 1\%$ of subjects who received pembrolizumab. The following section provides further guidance on the diagnosis and management of potential hepatic complications among HCC subjects.

a. Hepatitis B Flare

Hepatitis B flares are characterized by rapid elevations of ALT and AST to >5×ULN and/or >3× baseline. ALT elevation to ≥10×ULN is common. In the absence of hepatic decompensation, ALT/AST elevations are typically isolated (i.e., limited/no elevations of bilirubin/ALP). Subjects who are compliant with anti-viral therapy should have continued suppression of HBV DNA at the time of flare; thus, detection of HBV DNA should prompt questioning of subjects for compliance. Laboratory abnormalities secondary to flare are typically observed for 3-5 weeks.

Among subjects with HBV, a flare should be considered if this pattern is observed and there is no evidence of an alternative etiology. Guidelines for subjects with a diagnosis of HBV flare are as follows:

- Care should be instituted in consultation with a hepatologist (if necessary).
- For subjects who have detectable HBV DNA, re-institute anti-viral therapy.

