- If the subject is clinically stable, pembrolizumab dosing may be interrupted for up to 12 weeks. Subjects should undergo weekly laboratory tests including: AST, ALT, ALP, T-bil, D-bil, INR, HBsAg, HBV DNA (if detected at the onset of the flare). Obtain anti-HBe antibody, anti-HBs antibody, and HBV DNA levels (if not detected at the onset of the flare) every 2-3 weeks.
- If ALT returns to normal or Grade 1 (if normal at baseline), or to baseline grade (if Grade 2 at baseline) within 12 weeks, and subjects are clinically stable, subjects may restart pembrolizumab treatment. If these conditions are not met, then pembrolizumab treatment should be permanently discontinued.

b. Hepatitis C Recurrence or Flare

Subjects who achieved SVR 12 or SVR 24 and subjects with ongoing HCV infection are eligible for enrollment. In rare circumstances, HCV subjects who achieve SVR 12 or SVR 24 may relapse at later time points. Relapse is characterized by detection of HCV RNA, often accompanied by ALT elevations

Protocol/Amendment No.: 394-06

to >5×ULN. In the absence of hepatic decompensation, ALT/AST elevations are typically isolated (i.e., limited/no elevations of bilirubin/ALP).

Among subjects with uncontrolled hepatitis C, virologic flares are possible. Hepatitis C flares are characterized by rapid elevations of ALT and AST to >5×ULN and/or >3× baseline along with a rise in HCV RNA. ALT elevation to ≥10×ULN and a 1 log elevation in HCV RNA level are common. In the absence of hepatic decompensation, ALT/AST elevations are typically isolated (i.e., limited/no elevations of bilirubin/ALP). Laboratory abnormalities secondary to flare or recurrence are typically observed for 3-5 weeks.

Guidelines for subjects with recurrent HCV infection or an HCV flare are described below:

i. Recurrent HCV infection:

If the subject entered the study with an HCV RNA test of "Target not Detected" and has confirmed detectable HCV RNA (2 specimens, 1 week apart), then the subject has experienced a late HCV relapse or a recurrent infection.

- Question the subject about use of injection or inhalation drugs
- At the time of first detection of HCV RNA, send a specimen for HCV genotyping
- Measure AST, ALT, ALP, T-bil, D-bil, and INR weekly
- Measure HCV RNA levels every 2 weeks
- Therapy with HCV anti-viral treatments should be strongly considered.

i. HCV Flare:

- At the time of first detection of HCV RNA, send a specimen for HCV genotyping

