- Measure AST, ALT, ALP, T-bil, D-bil, INR weekly
- Measure HCV RNA levels every 2 weeks
- Therapy with HCV anti-viral treatments should be strongly considered.
- ii. For both recurrent infection and HCV flare: if ALT returns to normal or Grade 1 (if normal at baseline), or to baseline grade (if Grade 2 at baseline) within 12 weeks, and the subjects are clinically stable, subjects may restart pembrolizumab treatment. If these conditions are not met, then pembrolizumab treatment should be permanently discontinued.

Protocol/Amendment No.: 394-06

c. Immune-related hepatitis

i. Description: Immune-related hepatitis due to pembrolizumab should be suspected if:

- AST or ALT baseline values are less than 2×ULN, and AST or ALT laboratory values increase to ≥5×ULN
- Among subjects with baseline ALT or AST $\ge 2 \times ULN$, levels increase to $> 3 \times ULN$ the baseline level
- AST/ALT >500 U/L regardless of baseline level
- Among subjects with baseline T-bil levels <1.5 mg/dL: a value of >2.0 mg/dL
- Among subjects with baseline T-bil levels that are ≥ 1.5 mg/dL: a value of $\ge 2 \times$ the baseline level, OR
- Total bilirubin >3.0 mg/dL regardless of baseline level.

Immune-related hepatitis is a diagnosis made after excluding other possible etiologies for the change. Viral flare (if applicable), biliary or vascular obstruction, infection, medications, and alcohol use must be ruled out (see below).

ii. Management

- Interrupt pembrolizumab treatment and alert the sponsor as per ECI criteria above for ALT, AST, bilirubin, and hepatic decompensation.
- For Grade 2 AST / ALT elevation or increased bilirubin, administer corticosteroids (initial dose of 0.5-1mg/kg prednisone or equivalent) followed by taper.
- For Grade 3-4 AST / ALT elevation or increased bilirubin, administer corticosteroids (initial dose of 1-2mg/kg prednisone or equivalent) followed by taper.
- Monitor with liver function tests (consider weekly or more frequently until liver enzyme value returned to baseline or is stable).
- If symptoms and laboratory tests resolve to Grade ≤1 or baseline (if abnormal at baseline), taper steroids over 28 days. Study treatment may be restarted after steroid treatment has been tapered to prednisone ≤10 mg/day (or equivalent dose of another agent). Treatment and laboratory results must be reported on a case report form (CRF).

Protocol/Amendment No.: 394-06

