Additionally, any serious adverse event, considered by an investigator who is a qualified physician to be related to the Sponsor's product that is brought to the attention of the investigator at any time following consent through the end of the specified safety follow-up period specified in the paragraph above, or at any time outside of the time period specified in the previous paragraph also must be reported immediately to the Sponsor.

All subjects with serious adverse events must be followed up for outcome.

7.2.3.2 Events of Clinical Interest.

Selected non-serious and serious adverse events are also known as Events of Clinical Interest (ECI) and must be reported to the Sponsor.

For the time period beginning when the consent form is signed until treatment allocation/randomization, any ECI, or follow up to an ECI, that occurs to any subject must be reported within 24 hours to the Sponsor if it causes the subject to be excluded from the trial, or is the result of a protocol-specified intervention, including but not limited to washout or discontinuation of usual therapy, diet, placebo treatment or a procedure.

For the time period beginning at treatment allocation/randomization through 14 days following cessation of treatment, any ECI, or follow up to an ECI, whether or not related to

MK-3475-394-06 Final Protocol 03-Nov-2022 Confidential

Protocol/Amendment No.: 394-06

the Sponsor's product, must be reported within 24 hours to the Sponsor, either by electronic media or paper. Electronic reporting procedures can be found in the EDC data entry guidelines. Paper reporting procedures can be found in the Investigator Trial File Binder (or equivalent).

Events of clinical interest for this trial include:

- 1) An overdose of Sponsor's product, as defined in Section 7.2.1 Definition of an Overdose for This Protocol and Reporting of Overdose to the Sponsor, that is not associated with clinical symptoms or abnormal laboratory results.
- 2) Hepatic ECIs include any of the following events. All of these events will require holding study treatment, notification of the event(s) to the Sponsor within 24 hours via electronic media or paper, and a hepatology consultation if necessary. For dose interval modification, refer to Section 5.2.1.2. For guidance related to the diagnosis and management of hepatic ECIs, refer to Section 5.2.1.3.

a. ALT:

- i. Among subjects with baseline ALT $<2\times$ ULN: ALT $\ge 5\times$ ULN

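### After a hepatitis B flare or a hepatitis C recurrence or flare, the restart rule tests only ALT and clinical stability, so read literally it can clear a subject whose AST or bilirubin still meets a hold criterion

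*Protocol*

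**What the plan says.** **Hold.** Protocol Section 5.2.1.3 opens with the hepatic events of clinical interest (ECIs). ALT, AST and total bilirubin each have their own criteria, and clinical decompensation is a fourth group. For all of them the text says "All of these events will require holding study treatment". Section 7.2.3.2 repeats the list and the instruction: "All of these events will require holding study treatment, notification of the event(s) to the Sponsor within 24 hours". Neither place gives a general rule for releasing the hold.

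**Flare definitions.** Part a says "Hepatitis B flares are characterized by rapid elevations of ALT and AST". Part b says "Hepatitis C flares are characterized by rapid elevations of ALT and AST", together with a rise in HCV RNA. HCV relapse is described by HCV RNA, often with raised ALT; AST is not in that description.

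**Restart.** For hepatitis B, part a reads "If ALT returns to normal or Grade 1 (if normal at baseline", then adds return to baseline grade for subjects at Grade 2 at baseline, all within 12 weeks and with the subject clinically stable. Such subjects may restart. Part b has the same test for recurrence and flare: "if ALT returns to normal or Grade 1 (if normal at baseline". Both parts end with the same consequence: "If these conditions are not met, then pembrolizumab treatment should be permanently discontinued". Part a alone also caps the interruption: "pembrolizumab dosing may be interrupted for up to 12 weeks".

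**Monitoring.** AST, ALT, ALP, total and direct bilirubin and INR are drawn weekly in both pathways.

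**The concern.** The criteria that stop dosing and the criteria that restart it do not match. Three laboratory measures can trigger the hold, but only one is tested for release. A clinically stable subject whose ALT has recovered meets every named restart condition even if AST or bilirubin is still at a level that, at the start of the same section, requires holding study drug.

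Two sites could then treat the same subject differently. One takes part a or b as clearance to restart; the other keeps holding under the opening list. At stake is re-exposure of a subject with liver disease to a drug that can itself cause hepatitis, while a protocol-defined hepatic hold criterion is still present. The rule covers a substantial group: HBV etiology is a stratification factor, and both controlled HBV infection and untreated HCV infection are eligible.

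**Working it through.** The plan has no figure to reproduce here. The check compares the rules within Section 5.2.1.3 and then looks elsewhere for text that would close the gap.

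**1. Rules side by side**

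| Pathway | Laboratory condition for restart | Time limit |
|---|---|---|
| Part a, HBV flare | ALT only | 12 weeks for ALT recovery; interruption also capped at 12 weeks |
| Part b, HCV recurrence or flare | ALT only | 12 weeks for ALT recovery; no interruption cap stated |
| Part c, immune-related hepatitis | Laboratory tests generally, to Grade 1 or lower or baseline | 3 weeks for laboratory recovery; 12 weeks for steroid reduction |
| Part d, other hepatic ECIs | Laboratory values generally, to Grade 1 or baseline | 3 weeks |

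No reason is given for using ALT alone in parts a and b.

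**2. Which subjects are exposed**

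AST hold criteria (opening list): at least 5×ULN when baseline is below about 2×ULN; more than 3× baseline when baseline is 2×ULN or higher; more than 500 U/L at any baseline. Flare wording: more than 5×ULN and/or more than 3× baseline.

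- Baseline AST 1×ULN: the hold starts at 5×ULN, and the flare wording is met above 3 × 1 = 3×ULN. AST of 6×ULN meets both. AST of 3.5×ULN fits the flare wording but meets no AST hold. So not every flare sets off an AST hold.
- Baseline AST 5×ULN, the entry ceiling in Table 1: the relative hold is above 3 × 5 = 15×ULN. The 500 U/L criterion comes first if the ULN exceeds 500/15 = 33.3 U/L. The documents give no ULN. For an assumed ULN of 35 to 50 U/L, 500 U/L is 500/35 = 14.3×ULN to 500/50 = 10.0×ULN.
- Bilirubin, baseline 1.4 mg/dL: the hold starts above 2.0 mg/dL, so 2.1 mg/dL (a rise of 0.7) meets it. Part a expects limited or no bilirubin rise in a flare without decompensation, so this is the less typical route.

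**3. Does other text supply the missing condition?**

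- *Part c* applies only after viral flare has been ruled out.
- *Part d* is headed as covering other hepatic ECIs, and its 3-week limit cannot coexist with the 12-week window in parts a and b. Its imaging work-up for raised bilirubin would partly catch a bilirubin rise that outlasts ALT.
- *Permanent-discontinuation list, Section 5.2.1.3.* It names ALT above 20×ULN but no AST or bilirubin level. Its recurrence item is confined to events presumed immune-related.
- *Child-Pugh score of 9 or more.* Subjects enter as class A, 5 to 6 points. Bilirubin above 3.0 mg/dL scores 3 points instead of 1, adding at most 2: 5 + 2 = 7, 6 + 2 = 8, both below 9. AST is not scored. Neither measure alone triggers this stop.
- *Clinical stability.* The only definition is in Section 7.1.4.7, for continuing treatment after radiologic progression. It concerns worsening laboratory values, not persisting ones.
- *Section 7.1.3.1* requires laboratory results to be acceptable before each dose but gives no threshold.
- *Sections 5.8.1 and 7.1.1.9* bear on a prolonged hold. The first lists discontinuation for unacceptable adverse events, for intercurrent illness that prevents dosing, and for a condition placing the subject at unnecessary risk. The second requires a documented investigator–Sponsor decision for gaps over 12 weeks that are administrative or not drug-related. Neither sets a laboratory condition.

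None of these puts AST or bilirubin into the part a or part b restart test.

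**The case against.** The strongest reply is that there is no true conflict. The hold is mandatory and the restart wording is permissive, and a permission does not cancel a standing hold. On that reading the protocol already forbids dosing while an AST or bilirubin criterion is met. This is a fair reading, and it defeats the inference that the protocol instructs sites to re-dose during an active hold; it does not. What remains is that the text never says which rule governs, and the specific rule, read alone, gives clearance.

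A second reply concerns the 12-week point. A reader might infer that the plan has no rule at all for a subject whose ALT has recovered but whose AST has not. The documents do not support that: Sections 5.8.1 and 7.1.1.9 give judgement-based routes. Nor does the 12-week interruption cap carry over to hepatitis C, because it appears only in part a; in part b, 12 weeks limits ALT recovery only. A tidy count of which ALT and AST combinations have a stated outcome would also be unsafe, because parts a and b define ALT recovery for baseline normal and baseline Grade 2 but not for baseline Grade 1.

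Third, the scenario may be rare. Flare abnormalities are said typically to last 3 to 5 weeks, and the documents do not report AST staying raised after ALT recovers. Liver panels every cycle, Child-Pugh collection until the event resolves, and reporting of every retreatment to the Sponsor make unnoticed re-dosing less likely. All of this stands. It lowers the priority but does not supply the missing condition.

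**Conclusion.** The point holds as a narrow gap in a safety rule. In parts a and b of Section 5.2.1.3 the stated restart test is ALT plus clinical stability. Read literally, it clears a stable subject while an AST hold criterion, or less typically a bilirubin one, is still met. Parts c and d do not share this feature.

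The size cannot be stated as a rate: the documents give neither the flare frequency nor how often AST or bilirubin outlasts ALT. The conclusion rests on the wording alone. The ULN range used above is assumed and serves only to show where the hold levels fall. Existing safeguards limit the risk. Sample size, power, type I error and the estimand are untouched. This is a cheap patient-safety improvement of low priority.

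**What to change.** In parts a and b, add to the ALT and clinical-stability conditions, inside the same 12-week limit: *and no hepatic ECI laboratory criterion for ALT, AST or total bilirubin listed at the start of Section 5.2.1.3 is still met*. The discontinuation sentence already in each part then also covers a criterion that persists at 12 weeks. A stricter requirement, with AST and bilirubin back to Grade 1 or baseline, is optional and not needed to close the gap.

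The cost is one clause in each part and no new tests, because AST and bilirubin are already drawn weekly. Subjects whose AST and bilirubin are raised but below every hold level are not affected by the clause. The downside is that a few subjects would restart later, or would be discontinued at 12 weeks where case-by-case judgement now applies. If the Sponsor wants to keep that judgement, the clause should say that a criterion persisting at 12 weeks is decided by documented consultation.

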5.2.2 Timing of Dose Administration

Cycle 1, Day 1 treatment with study drug should begin on the day of randomization, but no later than 3 days from the date the subject is randomized to study treatment. However, every effort should be made to begin trial treatment on the day of randomization.

For all additional cycles of study treatment, treatment may be administered up to 3 days before or 3 days after the scheduled Day 1 of each cycle due to administrative reasons per the investigator's judgment.

All study treatments will begin on Day 1 of each cycle after all pre-dose study procedures and assessments have been completed as detailed on the Trial Flow Chart –Section 6.0.

Protocol/Amendment No.: 394-06

Study treatment will be administered as a 30 minute IV infusion every 3 weeks. Sites should make every effort to target infusion timing to be as close to 30 minutes as possible. However, given the variability of infusion pumps from site to site, a window of -5 min and +10 min is permitted (i.e., infusion time is 30 minutes: -5 min/+10 min).

The Pharmacy Manual contains specific instructions for the preparation of the study treatment infusion fluid and administration of infusion solution.

5.2.3 Trial Blinding

A double-blinding technique with in-house blinding will be used. Pembrolizumab and placebo will be packaged identically so that blind is maintained. The subject, the investigator and Sponsor personnel or delegate(s) who are involved in the treatment or clinical evaluation of the subjects are unaware of the group assignments.

See Section 7.1.5.2, Blinding/Unblinding, for a description of the method of unblinding a subject during the trial, should such action be warranted.

5.3 Randomization

Treatment allocation/randomization will occur centrally using an interactive voice response system / integrated web response system (IVRS/IWRS). There are 2 treatment arms. Subjects will be assigned randomly in a 2:1 ratio to pembrolizumab and placebo, respectively.

5.4 Stratification

Treatment allocation/randomization will be stratified according to the following factors:

- 1) Prior treatment (sorafenib vs. chemotherapy)
- 2) Macrovascular invasion: (Yes vs. No)
- 3) Etiology (HBV vs. others (HCV, non-infected))

5.5 Concomitant Medications/Vaccinations (Allowed & Prohibited)

Medications or vaccinations specifically prohibited in the exclusion criteria are not allowed during the ongoing trial. If there is a clinical indication for any medication or vaccination specifically prohibited during the trial, discontinuation from trial therapy or vaccination may be required. The investigator should discuss any questions regarding this with the Sponsor Clinical Director. The final decision on any supportive therapy or vaccination rests with the investigator and/or the subject's primary physician. However, the decision to continue the subject on trial therapy or vaccination schedule requires the mutual agreement of the investigator, the Sponsor and the subject.

Protocol/Amendment No.: 394-06

